1.2 Trial design

A two stage, open label, randomized (1:1:1) controlled trial with formal interim analysis after 171 participants (57 per arm) which also includes an informal interim analysis after 30 participants (10 per arm) complete follow-up. Due to the three different stages in this trial, the MATIS SAP is separated into two sections. The aim of this statistical analysis plan (SAP) is to describe in detail the analysis that will be undertaken for the formal interim analysis and final analysis. The informal interim analysis was to provide an early opportunity to check the dosing regimen, see MATIS SAP I – Dose Verification for a detailed description of the statistical analysis conducted at this stage.

[figure not shown]

Figure 1: Schematic of study Design

Treatment is for 14 days from baseline. Patients will receive follow-up assessments at 1, 7, 14 and 28 days after the first dose. The time allowed for screening assessments allows time for eligibility assessments to be included.

- Screening Period: up to 7 days to the day of randomisation
- Treatment Period: 14 days
- Follow-up period: Day 14 to 28

Patients who have recovered and are fit for discharge from hospital during the treatment period, will be discharged home with trial medication to complete a fixed 14 day course. Such patients will be followed up weekly with telephone monitoring until day 28 and additional blood test monitoring where practically possible.

Table 1. Study visits

Table 1. Study visits	Screening	Baseline				Last
Study Day	-6 to 0	0	1+	7 #	14#	visit 28 #
Time window		-2 days	+1	± 3	± 3	± 3
		,	day	day	day	day
Informed consent	X					-
Inclusion/Exclusion criteria	X	X				
Demographic data	X					
Medical history including major	X					
comorbidities						
Physical exam	X					
COVID-19 diagnosis, duration and	X					
severity						
Pregnancy test	X					
Vital signs	X	X	X	X	X	X
NEWS score	X	X	X	X	X	X
Inflammatory markers (CRP, D-dimer,		X	X	X	X	X
LDH, ferritin, full blood count)						
PK levels*					X	X
Full blood count¶		Daily while on CYP3A4 inhibitor				
FiO ₂	X	X	X	X	X	X
SpO ₂ and/or PaO ₂	X	X	X	X	X	X
Randomisation		X				
Weight and Estimated height		X				
Safety monitoring of liver and renal	X	X	X	X	X	X
function						
Length of stay						
Serious Adverse Events	X	X	X	X	X	X
Concomitant medications	X	X	X	X	X	X
Serum		X		X		X
Plasma		X		X		X
RNA in PAX gene tube		X		X		X
PBMC		X		X		X
Nasosorption biomarkers		X		X		X

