1.4.5 Treatment duration

The planned duration of treatment is 14 days. Participants may be discontinued from treatment earlier due to unacceptable toxicity or disease progression, which will be recorded as serious adverse events (SAEs). If a participant is discharged prior to day 14 they will go home and continue with the treatment plan.

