1.5 Sample size estimation

In the following Stage 1 refers to the formal interim analysis after 171 participants have been recruited and completed 14 days of follow-up. Stage 2 refers to the final analysis when recruitment and follow-up are complete, and it includes all the participants.

171 (57 per arm) patients with COVID-19 pneumonia will be recruited to Stage 1, if the trial progresses to Stage 2 an additional maximum of 285 (95 per arm) will be recruited, resulting in a potential sample size of 456 if three trial arms continue for the whole trial (152 per arm). These numbers have been chosen to provide power of 90% (minimum marginal power) with a maximum 5% chance of an intervention arm being recommended when it provides no improvement over control (5% one-sided family-wise error rate) and has been inflated by 5% for missing outcome data. Patients will be enrolled into RUX, FOS or SOC groups, as shown in figure 1.

The trial is designed to compare two experimental treatment arms to a shared control arm, with equal treatment allocation over two unequally spaced stages. Stage one will be undertaken after 37.5% of maximum sample size have been recruited and completed follow-up. A separate stopping rule will be

used which means the trial will continue until a decision is made for all experimental treatment arms. The sample size in each stage is allowed to vary according to the number of treatments present. The sample size calculation is based on the calculation in the R Shiny app for multi-stage group-sequential multi-arm clinical trials for a Bernoulli distributed primary outcome found here https://mjgrayling.shinyapps.io/multiarm/ but with an inflation to allow for unequal allocation across stages (0.375 of maximum possible sample in stage 1 and 0.625 of sample in stage 2).

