1.5.1 Sample size for formal interim analysis (Stage 1)

Current rate of severe pneumonia in the standard of care is 50%. In the case that an experimental arm reduces this to 30% (relative risk, RR, 0.6), then the design provides a 92% chance (one-sided alpha of 0.25, equivalent to stopping for futility if the one-sided p-value is >0.25) of it being recommended to continue to stage 2.

The design recommends stopping an intervention arm at stage 1 if the one-sided p-value is >0.25 but this is a non-binding rule (i.e. the overall power is calculated assuming this rule is always followed and the family-wise error rate (FWER) is calculated assuming it is not followed). The actual FWER will be lower if the rule is always followed).

Recruitment to the trial will continue during this interim analysis stage.

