A sensitivity analysis on the primary analysis will be undertaken if greater than 5% of outcome data are missing to examine the missing at random assumption. We will examine extreme examples assuming 1) that all participants with missing outcome had poor outcome e.g. all missing >=5, and 2) that all participants with missing outcome had good outcome e.g. all missing <5.

i. Compliance

Adherence to assigned treatment (RUX and FOS) will be calculated for each participant as the proportion of dose received per day of the prescribed dose per day and presented as the percentage received. This will be summarised by treatment group as described in section 2.6 above.

To explore the impact of compliance with the planned treatment protocol, we will undertake a perprotocol analysis to examine the treatment effect in those that take most of the treatment. We will define 'per-protocol' population as individuals who receives $\geq 90\%$ of prescribed dose and refit the primary analysis model on this population.

ii. Time of enrolment

An exploratory analysis of the primary outcome will be undertaken in order to assess the impact of time of enrolment into the MATIS study. A categorical variable will be created by splitting the recruitment period into quartiles such that participants are grouped into approximately four equal sized groups based on time of enrolment into the MATIS study. A crude odds ratio will be calculated for each quartile.

All stage 1 analysis of the WHO COVID-19 grades will be completed by the independent statistician in Newcastle University to ensure the trial statistician remains blind and only DMC members will see these results.

3.1.3 Statistical model at stage 2

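### The stage 1 per-protocol analysis filters the drug arms on dose taken, which progression or death can itself reduce, so a supportive result shown to the DMC can be biased towards the drug

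*SAP*

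**What the plan says.** SAP 3.1.2 i (Compliance) measures adherence to RUX and FOS as the percentage of the prescribed daily dose received. It then plans to "undertake a perprotocol analysis to examine the treatment effect in those that take most of the treatment", defined as at least 90% of prescribed dose, with the primary model refitted in that set. It does not say whether days after a stop or death count as prescribed days, or how SOC patients enter the set. For adherence it points to SAP 2.6, which refers on to SAP I, a separate document.

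SAP 1.4.5, like protocol 7.16, states: "Participants may be discontinued from treatment earlier due to unacceptable toxicity or disease progression". The primary outcome (SAP 3.1.1) is progression to a score of 5 or more, including death, within 14 days.

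SAP 3.1.2 says that the DMC sees the stage 1 analyses of the WHO grades. SAP 1.8 bases continuation on one-sided p<=0.25 in an ITT analysis. Protocol 4.1 calls this threshold suggested and wants the p-value read on a continuous scale. SAP 1.5.1 makes the rule non-binding. At stage 2, compliance is handled by a CACE analysis instead (SAP 3.1.5 iii), which assumes SOC to be fully compliant.

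**The concern.** A per-protocol set is chosen after randomisation. Here the selecting variable, dose received, can be changed by the outcome: a patient who progresses and is taken off drug, or who dies, may fall below 90% for that reason. A SOC patient with the same course has no study dose to fall short of and stays in. The comparison then sets a drug arm with some of its events removed against a SOC arm with all of them.

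The propensity score in the stage 1 model uses baseline status and treatments given up to one day after randomisation. It cannot correct selection on a later outcome.

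At stake is the reading of a borderline arm. If the ITT result narrowly misses 0.25 and a supportive analysis appears to show benefit, the DMC has latitude to continue an arm that does nothing.

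**Working it through.** **Inputs from the documents.** "171 (57 per arm) patients with COVID-19 pneumonia will be recruited to Stage 1", and the size "has been inflated by 5% for missing outcome data": 57 × 0.95 = 54.15, so about 54 evaluable per arm. Event rates are 50% in SOC and 30% under the target effect, with a one-sided threshold of 0.25 (SAP 1.5.1). Doses come from SAP 1.4.3 and 1.4.4.

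**The plan's own figure.** With 54 per arm, SE = √(0.25/54 + 0.21/54) = 0.0923. The chance of passing stage 1 is Φ(0.20/0.0923 − 0.674) = Φ(1.49) = 93%. The SAP states 92%, so the basis agrees.

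**How strict 90% is, if the denominator is the full 14-day course.**
- RUX: 7 × 20 + 7 × 10 = 210 mg. Stopping after day 11 gives 180/210 = 85.7% (excluded); after day 12, 190/210 = 90.5% (kept).
- FOS: 7 × 300 + 7 × 200 = 3,500 mg. Stopping after day 12 gives 3,100/3,500 = 88.6% (excluded); after day 13, 3,300/3,500 = 94.3% (kept).

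On that denominator, nearly everyone who dies or is taken off drug at progression leaves the drug arm.

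**Effect on a drug with no benefit.** Assume 50% events in both arms and all SOC patients kept. Let f be the share of drug-arm progressors excluded and g the share of non-progressors excluded. Neither is given in the documents, so both are assumed over a range. The expected OR is (1−f)/(1−g).

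With 27 expected events and 27 expected non-events per arm, SE(log OR) = √[1/(27(1−f)) + 1/(27(1−g)) + 2/27], and the chance of one-sided p<=0.25 is about Φ(−log OR/SE − 0.674). For f = 30%, g = 0: log OR = −0.357, SE = √(1/18.9 + 3/27) = 0.405, giving Φ(0.881 − 0.674) = 58%.

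Simulation of the unadjusted Wald test gives:

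| f | g | Expected OR | Chance of p<=0.25 | Same, given ITT misses 0.25 |
|---|---|---|---|---|
| 10% | 10% | 1.00 | 25% | 4% |
| 10% | 0 | 0.90 | 35% | 13% |
| 25% | 10% | 0.83 | 41% | 22% |
| 30% | 0 | 0.70 | 58% | 45% |
| 50% | 10% | 0.56 | 76% | 68% |

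The reverse case, f = 10% and g = 20%, has OR 0.90/0.80 = 1.13. With SE = √(1/24.3 + 1/21.6 + 2/27) = 0.402, the chance is Φ(−0.118/0.402 − 0.674) = 17%, so the bias then runs against the drug.

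**The case against.** The strongest reply is that this analysis decides nothing. Continuation rests on the ITT p-value, the refit is introduced as exploratory, and the DMC also receives adherence summaries (SAP 2.6), in which unequal exclusion could be seen. This stands. A reader might infer that the filter corrupts the futility rule or raises the false-positive rate of the trial. The documents do not support that: SAP 1.5.1 computes the FWER as if the futility rule were not followed, so wrongly continuing an arm costs patients and time, not type I error.

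A reader might also infer that treatment stops whenever a patient progresses. The text only permits it, and protocol 7.4 foresees fostamatinib by feeding tube in intubated patients. Only death necessarily ends dosing.

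The unfiltered SOC arm is an inference at stage 1. It is the natural one, since no SOC adherence measure is defined, and the stage 2 text makes the matching assumption explicit.

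Non-progressors can fall below 90% too, through home dosing after discharge or through interruptions and reductions for toxicity (protocol 7.5, 7.7, 7.8). That narrows the gap between f and g and could reverse it. If days after a stop or death are not counted as prescribed, the bias from stopping disappears. These points limit the size of the problem. They do not make the set free of selection on the outcome.

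**Conclusion.** The point holds as a conditional one. As written, the SAP allows a stage 1 per-protocol set in which drug-arm membership depends partly on the primary outcome while SOC keeps all its events. If post-stop days count and progressors are excluded more often than non-progressors, a drug with no effect has a 35% to 76% chance of p<=0.25 in this analysis over the unequal exclusion rates in the table, against 25% on all randomised patients. With balanced exclusion there is no bias.

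It would be too strong to say that the analysis makes a useless drug look promising: f, g, the denominator and the SOC handling are all unstated. The consequence is a potentially misleading supportive result in front of a DMC with discretion. The formal decision rule and the final error rate are intact. The change is worth making before the interim data are analysed.

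**What to change.** At stage 1, drop the 90% filter, or replace it with a randomisation-based CACE estimate that keeps all randomised patients and codes study-drug exposure as zero in SOC. The simplest form divides the ITT risk difference by the difference between arms in the proportion exposed, so it is zero whenever the ITT difference is zero. The log-link residual-inclusion version planned for stage 2 lacks that exact property when adherence depends on the outcome, so the risk-difference form is the safer choice here.

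If a per-protocol view is kept, the SAP should state the adherence denominator and how SOC enters the set, and label the result descriptive and not for the continuation decision. Counting dose only up to the event should not be the main remedy: early progressors have few days in which to miss doses, so they may be kept preferentially and the bias may turn against the drug.

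The cost is SAP wording and a small programming change. One familiar analysis is lost, and a CACE estimate from about 54 per arm will be imprecise.

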#### 2 STUDY OBJECTIVES

#### 2.1 PRIMARY OBJECTIVE

The primary objective is to determine the efficacy of RUX and FOS to reduce the proportion of hospitalised patients progressing from mild/moderate to severe COVID-19 pneumonia. A modified WHO COVID-19 Severity Ordinal Scale (COVID-19 Therapeutic Trial Synopsis published 18th February 2020) will be used to grade clinical deterioration from Hospitalised Mild Disease (<5) to Hospitalised Severe Disease (≥ 5). The modification includes an additional grade for Hospitalised Severe Disease that allows the capture of clinical deterioration in patients for whom escalation in organ support is not offered. Patients are eligible for recruitment to MATIS at grades 3 or 4. These patients stand to gain the greatest benefit from inflammatory signal inhibitors that may ameliorate the cytokine storm and prevent organ failure.

Table 1. Modified WHO COVID-19 Severity Scale, from the WHO R&D Blueprint

Patient state Descriptor		Grade
Uninfected	No clinical or virological evidence of infection	0
Ambulatory	No limitation of activities	1

MATIS version 4.0 dated 2nd November 2022

IRAS: 282552 Page **20** of **57** 

	Limitation of activities	2
Haspitalisad mild disease	Hospitalised, no oxygen therapy	3
Hospitalised mild disease	Oxygen by mask or nasal prongs	4
	$SpO_2$ < 90% on $FiO_2$ $\geq$ 60% by face mask	5
Hospitalised severe disease	Non-invasive ventilation, CPAP or high-flow oxygen	6
	Intubation and mechanical ventilation	7
	Ventilation + additional organ support (vasopressors, RRT, ECMO)	8
Dead	Death	9

Published in the COVID Therapeutic Trial Synopsis, February 18th 2020

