In Stage 2 a logistic regression model will be used to assess the treatment effect of RUX and FOS compared to SOC. The model will include the treatment arms, baseline modified WHO Severity Score, trial co-enrolment at baseline, and randomisation stratification variables viz. site and age (<65 vs ≥65). As well as reporting OR and 95% CIs, the model will be used to estimate the difference in proportion of participants with modified WHO COVID-19 Ordinal Score ≥5. The treatment effect in the absence of post-randomisation co-enrolment and receipt of rescue medication will be estimated in a supplementary analysis where participants' outcomes after either will be treated as missing and a controlled multiple imputation using a delta based approach will be used.

For the primary outcome, progression to severe COVID-19 disease within 14 days, discharge alive from the admitting hospital before 14 days will assume safety from the event (in the absence of additional data confirming otherwise). An additional sensitivity analysis will be performed if there is a change of dose after review of the first thirty patients.

For time-to-event analyses required for secondary endpoints such as time to discharge, each treatment group will be compared with SOC and modelled using a proportional hazards time-to-event model adjusted for randomisation stratification variables. Kaplan-Meier estimates for the time to event will also be plotted (with confidence intervals). The log-rank 'observed minus expected' statistic (and its variance) will be used to estimate the average event rate ratio (and its confidence interval) for those allocated to each treatment group versus the no additional treatment group.

Pre-specified subgroup analysis will be conducted for the primary outcome using the statistical test for interaction (or test for trend where appropriate) for the following: disease severity as graded by the WHO

MATIS version 4.0 dated 2nd November 2022

IRAS: 282552 Page **28** of **57** 

Imperial College Healthcare

COVID-19 Ordinal Severity Scale; time since onset of symptoms; sex; age; and comorbidities obesity, chronic heart, lung, kidney and liver disease, diabetes, immunocompromised and smoking status. Pre-specified subgroup analyses will also be conducted for the primary outcome using the statistical test for interaction (or test for trend where appropriate) for patients with admission CRP >200mg/L and/or D-dimer 2500ng/mL.

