1.3 Study population

1.3.1 Eligibility criteria

Inclusion criteria

- Patients age ≥ 18 years at screening.
- Patients meeting criteria of:
 - o Hospitalization AND
 - o SARS-CoV2 infection (clinically suspected¹ or laboratory confirmed) AND
 - o Radiological change consistent with COVID-19 disease
- Mild or moderate (Grade 3 or 4 severity by modified WHO COVID-19 Ordinal Scale) C19 pneumonia.
- $CRP \ge 30 \text{mg/L}$ at any time point.
- Informed consent from patient or personal or professional representative.
- No medical history that might, in the opinion of the responsible clinician, put the patient at significant risk if he/she were to participate in the trial.
- Agreement to abstain from sexual intercourse or use contraception that is >99% effective for all participants of childbearing potential for 42 days.²
- For male participants, agreement to abstain from sperm donation for 42 days after the last dose of study drug.³
- Non-English speakers will be able to join the study. If patients are unable to understand verbal
 or written information in English hospital translation services will be requested at the
 participating site for the participant where possible.
- Patients normally on non-invasive ventilation such as continuous positive airway pressure (CPAP) at home are eligible.

¹ Clinical suspicion of COVID-19 pneumonia will be confirmed by two independent clinicians.

² Females must be either post-menopausal for at least 1 year or surgically sterile; or if female of child-bearing potential, must not be pregnant or lactating and must agree to use an acceptable method of birth control throughout the duration of the trial and for 30 days following the last dose. Acceptable methods of birth control are defined as: hormonal contraception (pill, injection or implant) used consistently for at least 30 days prior to enrollment, intrauterine device (IUD), double-barrier (ie, condom and spermicide, or condom and diaphragm), or true abstinence (when this is in line with the preferred and usual lifestyle of the subject).

³ Male subject with a partner of childbearing potential must agree to use an appropriate double-barrier method of contraception during the time interval between administration of the first dose of study drug and 30 days following the last dose, or must agree to true abstinence (when this is in line with the preferred and usual lifestyle of the subject).

Exclusion criteria

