1.6 Randomisation

Patients will be randomized to one of three actively recruiting trial arms, RUX, FOS or SOC. Eligible patients will be allocated using a central web-based randomisation service that uses randomisation sequences with random block sizes that are stratified by age ($<65 \text{ vs} \ge 65$) and site. If stage 2 occurs with one intervention arm stopped then the randomisation ratio will be 1:1.

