The stage two primary analysis will consist of fitting one binomial regression model regardless of whether one or two experimental treatments progress from stage one. Specifically a generalized linear model with WHO COVID-19 status (<5 or \ge 5) as the outcome and treatment group, baseline WHO COVID-19 score (3 or 4), age (<65 or \ge 65), receipt of known effective treatments dexamethasone and/or tociluzimab, prior vaccination against COVID-19 (y/n) and receipt of paxlovid and/or molnupiravir at the time of or prior to randomisation into MATIS as covariates will be fitted. Effective treatments will be included as separate covariates in the primary analysis model. Given the anticipated small number of sites in this study, site will also be included in the model as a fixed effect. In the event that all participants are on one of the effective treatments that covariate will be removed from the model.

If including site as a fixed effect results in unstable model estimates e.g. if there are a number of sites with very few randomisations we will exclude site from the model and we will only adjust for baseline WHO COVID score, age group, receipt of known effective treatments dexamethasone and/or tociluzimab, prior vaccination against COVID-19, and receipt of paxlovid and/or molnupiravir.⁶ We will also consider not adjusting for paxlovid and/or molnupiravir if the number of participants receiving these are low. If after removing sites and treatments the model is not stable due to event rate:covariate ratio we will adjust for all covariates using a propensity score approach.

The model will be fitted with a binomial distribution and logit link function and the treatment effect will be reported as an odds ratio with corresponding 95% confidence interval and p-values. P-values will be one-sided and judged at the 0.027 level. Therefore, a two-sided p-value < 0.054 will be used to indicate a significant treatment effect.

The stage two model to be fitted to estimate the treatment effects will be:

$$logit(\pi_{ij}) = \beta_{0} + \beta_{1}RUX_{ij} + \beta_{2}FOS_{ij} + \beta_{3}WHO_{ij}^{0} + \beta_{4}AGE_{ij}^{0} + \beta_{5}DEX_{ij}^{0} + \beta_{6}TOC_{ij}^{0} + \beta_{7}VAC_{ij}^{0} + \beta_{8}PAX_{ij}^{0} + \beta_{9}MOL_{ij}^{0} + \beta_{10}SITE_{1} + \beta_{11}SITE_{2} + \cdots + \beta_{12}SITE_{i-1}$$

 RUX_{ij} : dummy variable for treatment ($RUX_{ij} = 0$ or 1) for participant i in jth site

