 FOS_{ij} : dummy variable for treatment ($FOS_{ij} = 0$ or 1) for participant i in jth site

 WHO_{ij}^0 : dummy variable for baseline WHO COVID-19 value for participant i in jth site (WHO_{ij})

0 or 1 where 0 indicates score of 3 and 1 indicates score of 4)

 AGE_{ij}^{0} : dummy variable for age-group ($AGE_{ij} = 0$ or 1 where 0 indicates <

65 years and 1 indicates \geq 65) for participant i

 DEX_{ij}^0 : dummy variable for receipt of dexamethasone at the time of or prior to randomisation (includes day of randomisation or one day post randomisation) ($DEX_{ij} = 0$ or 1) for participant i

 TOC_{ij}^0 : dummy variable for receipt of tociluzimab at the time of or prior to randomisation (includes

day of randomisation or one day post randomisation) ($TOC_{ij} = 0$ or 1) for participant i

 VAC_{ij}^0 : dummy variable for prior vaccination against COVID-19 at the time of or prior to randomisation (includes day of randomisation or one day post randomisation) ($VAC_{ij} = 0 \ or \ 1$) for participant i

 PAX_{ij}^0 : dummy variable for receipt of paxlovid at the time of or prior to randomisation (includes day of randomisation or one day post randomisation) ($PAX_{ij} = 0 \text{ or } 1$) for participant i

 MOL_{ij}^0 : dummy variable for receipt of molnupiravir at the time of or prior to randomisation (includes day of randomisation or one day post randomisation) ($MOL_{ij} = 0$ or 1) for participant i $Site_j$: dummy variable for each of the jth sites

 π_{ij} : probability of WHO COVID-19 \geq 5 for the ith participant in jth site

To account for missing outcomes in the primary analysis model we will impute missing WHO COVID-19 status using multiple imputation under the assumption of missing at random (MAR) as described in the primary statistical model at stage 1 section 3.1.2 plus the imputation model will contain the following additional variables: prior vaccination against COVID-19, and receipt of paxlovid and/or molnupiravir at the time of or prior to randomisation into MATIS, plus post-randomisation receipt of paxlovid and/or molnupiravir. Multiple imputation will be used for the final analysis regardless of levels of missingness at this stage.

As well as reporting odds ratios and 95% CIs, the model will be used to estimate the difference in proportion of participants with modified WHO COVID-19 Ordinal Score ≥ 5 .

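### The stage 2 primary model adjusts for age only as under 65 or 65 and over, and for respiratory status only as WHO grade 3 or 4, so part of the baseline prognostic information the trial already collects goes unused

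*SAP*

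**What the plan says.** **Coding in the primary model.** SAP 3.1.3 fits one logistic model with WHO status "as the outcome and treatment group, baseline WHO COVID-19 score (3 or 4), age" group, treatments received, vaccination and site. In the equation the age term is a "dummy variable for age-group" (0 below 65, 1 from 65 up), and the respiratory term is a "dummy variable for baseline WHO COVID-19 value for participant i in jth site" (0 for score 3, 1 for score 4). The stage 1 propensity score and the imputation model (SAP 3.1.2) use the same two codings. Protocol 4.2 has the same age cut at 65: "The model will include the treatment arms, baseline modified WHO Severity Score, trial co-enrolment at baseline, and randomisation stratification variables viz. site and age".

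**Why age group is there.** SAP 1.6 describes "randomisation sequences with random block sizes that are stratified by age" and site, and SAP 1.8 gives stratification as the reason for adjusting for both.

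**What is collected.** The visit schedules (protocol Table 7, SAP Table 1) mark FiO2 at screening and baseline, together with SpO2 and/or PaO2. Age in years is not itemised, but the schedule lists "Demographic data" at screening and eligibility requires "Patients age ≥ 18 years at screening". Grade 4 on the modified scale is "Oxygen by mask or nasal prongs" (protocol 2.1), so it holds every level of conventional oxygen need below grade 5. Grade 5 is itself defined by SpO2 and FiO2.

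**What is not planned.** No primary, sensitivity, exploratory or subgroup analysis of the primary outcome names age in years or FiO2. The age subgroup in SAP 3.1.6 is again <65 vs ≥65.

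**The concern.** A cut at 65 treats a 30-year-old like a 64-year-old, and a 66-year-old like a 90-year-old. One category for conventional oxygen treats a patient on low-flow nasal oxygen like one just short of the severe threshold. If risk of progression varies within these groups, the model leaves that variation in the residual noise, and chance imbalance within the groups goes uncorrected. At stake is the precision of the primary comparison at a fixed sample size.

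The stratification argument explains why age group is in the model. It does not explain why age in years is left out, and baseline FiO2 is not discussed as a covariate at all. Elsewhere the SAP takes the finer approach: the laboratory models in 3.2.5 adjust for the measured baseline value, and 2.8 uses a distributional method for dichotomised blood results in order to keep power.

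**Working it through.** **1. The plan's own figures.** Inputs from SAP 1.5: 50% vs 30%; one-sided 0.25 at stage 1 and 0.027 at the end; 57 then 152 per arm, inflated by 5% for missing outcomes. That leaves 57 × 0.95 ≈ 54 and 152 × 0.95 ≈ 144 evaluable per arm. With unpooled variance 0.5×0.5 + 0.3×0.7 = 0.46:

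- Expected Z at stage 1: 0.2/√(0.46/54) = 2.167. At the end: 0.2/√(0.46/144) = 3.539.
- Critical values: 0.674 and 1.927. Correlation: √(54/144) = 0.612.
- Final test alone: Φ(3.539 − 1.927) = 94.6%.
- Passing both (bivariate normal): 89.9%, against 90% stated.
- Stage 1 alone: 93%, against 92% stated.
- Family-wise error for two comparisons sharing a control (correlation 0.5): 4.9%, against a maximum of 5%.

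These figures use no covariates, so the coding of age and oxygen status cannot make them wrong.

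**2. What finer adjustment could add.** The documents give no prognostic strength for age or FiO2, so this step rests on assumptions. Age is normal with mean 60 and SD 15. 80% of patients are at grade 4 with FiO2 between 0.24 and 0.60, and grade 3 is set at 0.21. Effects are linear on the logit. Each row is 4,000 simulated three-arm trials with 144 evaluable per arm, 50% vs 30%, both drugs effective, and a Wald test at one-sided 0.027. Efficiency is (mean Z with continuous terms ÷ mean Z with binary terms)².

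| OR per 10 years / per 0.1 FiO2 | Risk-score variance kept by binary terms | Power, binary | Power, continuous added | Power, continuous instead | Efficiency gain |
|---|---|---|---|---|---|
| 1.2 / 1.3 | 53% | 95.0% | 94.9% | 94.7% | 1.3% |
| 1.5 / 1.5 | 56% | 95.1% | 95.6% | 95.6% | 4.4% |
| 1.5 / 2.0 | 51% | 95.3% | 96.8% | 97.0% | 7.3% |
| 2.0 / 2.0 | 56% | 96.5% | 97.8% | 97.9% | 10% |

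Simulation error is about 0.3 points. If neither variable is prognostic, power is about 94% under either coding. A gain of 1.3% to 10% of 144 is worth about 2 to 14 evaluable patients per arm.

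**3. On the plan's own definition of power.** SAP 1.5.2 counts success as passing stage 1 and being recommended at the end. Leave stage 1 unchanged, multiply the final expected Z by √(1 + gain), and hold the correlation at 0.612:

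| Gain | Final expected Z | Final test | Two-stage |
|---|---|---|---|
| 0 | 3.539 | 94.6% | 89.9% |
| 1.3% | 3.562 | 94.9% | 90.1% |
| 4.4% | 3.616 | 95.4% | 90.5% |
| 7.3% | 3.666 | 95.9% | 90.8% |
| 10% | 3.711 | 96.3% | 91.1% |

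**4. Room for parameters.** Expected events at the design rates are 144 × (0.50 + 0.30 + 0.30) = 158. If one arm stops: 144 × (0.50 + 0.30) = 115. Protocol 1.3 puts deterioration needing ventilatory support at around 30%. With a 30% control rate and the same relative risk of 0.6 (so 18%), the counts are 144 × (0.30 + 0.18 + 0.18) = 95 with three arms and 144 × (0.30 + 0.18) = 69 with two.

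**5. Effect on the odds ratio.** Adding the continuous terms moved the average conditional odds ratio from 0.40 to 0.38 in the 1.5/1.5 scenario and from 0.37 to 0.33 in the 2.0/2.0 scenario. This reflects conditioning on more covariates and is not a larger treatment benefit.

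**The case against.** The strongest reply is that the gain is small and assumed. In the weakest scenario no power difference can be detected. In the stronger ones, an odds ratio of 2 per 0.1 FiO2 implies about 12 between FiO2 0.24 and 0.60 (2 to the power 3.6). The simulation also left out dexamethasone, tocilizumab, vaccination, antivirals and site. Where these track oxygen need or age, they already recover some of the information. All of this stands, and it limits the size of the point without removing it.

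The age-group term also stands: it is a stratification factor that both documents commit to adjusting for, so age in years should be added beside it and should not replace it. Grades 3 and 4 are the scale's own categories and not a cut made by the analyst. SpO2 is scheduled only as SpO2 and/or PaO2, so an SpO2/FiO2 ratio may not exist for everyone, and FiO2 alone is the safer covariate.

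Event counts could be well below 158, and SAP 3.1.3 already plans to drop covariates if the model is unstable. Mean filling of missing baseline values, as in SAP 3.1.2, would be crude for FiO2. A linear age effect is not certain either, because the scale was modified to capture patients who are not offered escalation. These points belong in the specification of the fix.

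**Conclusion.** The point holds as a modest loss of efficiency. The two binary terms keep about half (51% to 56%) of the variance of the assumed age-plus-FiO2 risk score. Restoring the rest is worth roughly 1% to 10% in effective sample size. At 50% vs 30% that is about 0 to 2 points of final-test power and up to about 1 point of two-stage power. These sizes depend on prognostic strengths that the documents do not supply, and on age in years being recorded, which is implied but not itemised.

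Three stronger inferences are not supported:

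- **That the comparison is biased.** Coarse coding of baseline covariates does not bias a randomised comparison.
- **That the trial is underpowered.** The 90% reproduces with no adjustment at all.
- **That the power gain is larger.** It would be if the effect were smaller: at 50% vs 35% final-test power is only about 75%, so the same efficiency buys more points. But the design alternative in both documents is 30%.

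This is a cheap improvement of low priority.

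**What to change.** In SAP 3.1.3, keep the age-group and WHO 3/4 terms and add age in years and baseline FiO2 as continuous covariates. Use linear terms, or another form fixed before unblinding, so that the form is not chosen from the results. Then:

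- bring the model description in protocol 4.2 into line;
- include both variables in the imputation model;
- state how missing baseline FiO2 is handled, since the overall mean would blur grade 3 and grade 4 patients;
- list FiO2 among the first covariates to be dropped under the existing instability rule;
- report the already planned risk difference beside the conditional odds ratio, which will sit further from 1.

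No new data collection is needed, given the schedule and provided age is held in years. The cost is a change of text in two documents, two parameters against about 158 expected events (about 115 if one arm stops, fewer if the control rate is lower), and reliance on an assumed functional form.
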